- Twice-per-week dosing on Days 1, 4, 8, and 11, no dosing on Days 12 to 21, in 21-day cycles

If a switch in dose and/or regimen is recommended, the first tested dose level in the new regimen must not exceed the highest tested daily dose or the weekly cumulative dose must be equal to or lower than the highest weekly cumulative dose of regimen(s) tested so far.

The selected M3258 dose and regimen (RDE) will be combined with dexamethasone for the expansion cohort (Part B).

Dexamethasone will be given at a cumulative dose of 40 mg/week:

- 20 mg/day at Days 1, 4, 8, 11, 15, 18, 22 and 25 in a 28-day cycle

OR

- 20 mg/day at Days 1, 4, 8, 11, 15, and 18 in a 21-day cycle (regimen with drug holiday)

Dose Escalation Part A

Participants with MM whose disease has progressed following > 3 lines of therapy and for whom no effective standard therapy exists (see definition in Section 5) will be enrolled in the dose-escalation part of this study. The first dose escalation cohort will receive M3258 at the starting dose of 10 mg QD as a single agent. For further dose cohorts, a SMC will meet and review all available data to provide recommendations on the next dose level. The MTD is defined by the SMC with a target DLT rate of 25%. The following prespecified doses of 10

mg, 20 mg (100% increase), 35 mg (43% increase) and 50 mg (30% increase) are planned unless MTD is reached. The SMC, following review of preliminary safety, tolerability, PK and Pd information, will recommend the dose and/or the switch to an alternative regimen pre-specified in this protocol for the next cohort as applicable.

This may include proposing smaller dose increases compared to the prespecified doses and deescalation of the dose potentially down to 1mg.

The SMC may also recommend expanding a given cohort at the same dose level.

If additional dose levels above 50 mg are justified following review of preliminary safety, tolerability, PK, and Pd information from the initial cohorts, a protocol amendment will be submitted.

Depending on the observed toxicity profile, the SMC may decide on different doses as prespecified and/or change to regimens specified in this protocol. However, escalation may not proceed to any dose higher than 50 mg. In case escalation is recommended to proceed to doses higher than 50 mg, an amendment will be submitted. At each dose level, the first participant enrolled will be observed for DLTs for at least 48 hours before further participants are enrolled.

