Dexamethasone may be dose reduced according to [Table 14A](#) and [Table 14B](#) or institutional guidelines, if applicable, for toxicities assessed as strictly related to dexamethasone. In those cases, where the toxicity cannot be attributed to dexamethasone, the dose of M3258 should be reduced first (see Section [6.9.1](#)).

Dose modification or deferral should always be discussed with the Sponsor Medical Responsible.

Organ involved	Specifics	Toxicity NCI-CTCAE v5.0 Grade	Management of Toxicity with permanent Discontinuation or Dose Interruption and Modification
Acute pancreatitis			Permanently discontinue dexamethasone.
Gastrointestinal	Dyspepsia, gastric, or duodenal ulcer,		Institute proton pump inhibitor.
	Gastritis (requiring medical management)	Grade 1-2	If symptoms persist or worsen despite measures, reduce dexamethasone by 50% (eg., 20 mg per week to 10 mg per week).
	Requiring hospitalization or surgery	Grade \geq 3	Hold dexamethasone until symptoms adequately controlled. Restart and reduce dexamethasone by 50% from initial dose along with the use of proton pump inhibitors.
Metabolic	Hyperglycemia	Grade \geq 2	Diet control and monitor closely.
		Grade \geq 3	Treat with insulin or oral hypoglycemics as needed.
			If uncontrolled despite these measures, reduce dexamethasone by 50% from initial dose.
Cardiovascular	Edema (limiting function and unresponsive to therapy or anasarca)	Grade \geq 2	Diuretics as needed and dose reduction by 50% should be considered. If edema persists despite these measures, consider reducing dexamethasone dose from 10 mg to 5 mg.
			Monitor closely (weekly weight, restrict hydration).
Musculoskeletal	Muscle weakness (interfering with function and/or interfering with activities of daily living)	Grade \geq 2	Reduce dexamethasone by 50%.
			In case of no improvement or worsening, further (50%) dose reduction is recommended. If weakness persists despite these measures, permanently discontinue dexamethasone.
Neurological	Confusion or mood alteration	Grade \geq 2	Hold dexamethasone until symptoms resolve. Restart and reduce dexamethasone by 50%. Upon worsening or no improvement, consider further reduction of dose to 5 mg. Permanently discontinue dexamethasone if symptoms recur.
Constitutional	Insomnia	Grade \geq 2	Advise dexamethasone administration in the morning only.
			If symptoms persist, reduce the dose by 50% (eg., 20 mg to 10 mg to 5 mg).

Modified from Palumbo and Gay, 2009

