Table 14B Recommended Dose Reduction for Dexamethasone

First Dose Reduction	Second Dose Reduction	Third Dose Reduction
Reduce dexamethasone by 50% from starting dose	Give dexamethasone only on Day 8, 15, 21	Discontinue dexamethasone

Refer to [Palumbo and Gay, 2009](#).

Part B

In the expansion cohorts, the SMC will also monitor the safety of the participants treated with M3258 at RDE in combination with 20 mg/day dexamethasone and will meet after 3, 6, and subsequently every 6 participants have finished the DLT period or discontinued, unless a change in dosing has occurred. In case dosing in the expansion cohort was changed, the next SMC will be held after 3 participants have finished the DLT period or discontinued. Thereafter the SMC will evaluate the safety after every 6 participants (see Section 10). The SMC can recommend continuing enrollment at the RDE, changing the dose, or stopping the expansion part of the study. The SMC decisions in the expansion phase will also be supported by Bayesian modeling. Study Intervention after the End of Study.

The Sponsor will not provide any additional care to participants after they leave the study because such care would not differ from what is normally expected for participants with MM.

Part A and B

If a participant receives M3258 QD and misses taking a scheduled dose of M3258, then within a window of 12 hours it is acceptable to replace the missed dose. If in the QD dosing regimen the window is more than 12 hours after the scheduled dose time, then the missed dose should not be taken, and participants should be instructed to take the next scheduled dose.

If a participant receives M3258 twice-per-week and misses taking a scheduled dose within a window of 24 hours, then it is acceptable to replace the missed dose. For the twice-per-week dosing regimens in case of a delay of the scheduled dose, the missed dose should be taken as soon as possible, but at least two days (minimum 36 h) before the next scheduled dose.

If a participant vomits after taking M3258, the participant should not repeat the dose, but resume dosing at the time of the next scheduled dose.

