9.3 Populations for Analyses

The analysis populations are specified below. The final decision to exclude participants from any analysis population will be made during a data review meeting prior to database lock.

Analysis Set	Description
Screening (SCR)	All participants, who provided informed consent, regardless of the participant's randomization and study intervention status in the study.
Safety (SAF)	All participants, who were administered any dose of any study intervention. Analyses will consider participants as treated.
DLT	The Dose Escalation Set will include all participants who received at least one dose of study intervention and meet at least one of the following criteria: 
 Experienced at least one DLT during the DLT period, regardless of the administered number of doses of study intervention/completion of the DLT period Received at least 80% of the planned cumulative dose and 80% of planned administrations of each treatment during the DLT period and completed the DLT period.
PK	All participants, who receive at least one dose of study intervention, have no clinically important protocol deviations or important events affecting PK, and provide at least one measurable postdose concentration. Participants will be analyzed per the actual study intervention they received.
Pd	All participants, who receive at least one dose of study intervention, have no clinically important protocol deviations or important events affecting Pd, and provide at least one measurable Pd endpoint postdose.

DLT = Dose-limiting toxicity; Pd = Pharmacodynamics; PK = Pharmacokinetics.

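### The dexamethasone reduction tables in Section 6.6 contradict the dexamethasone schedule in Section 4.1, and give different second steps with no rule on which governs

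*Protocol*

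**What the plan says.** Protocol Section 4.1 sets the Part B background drug: "Dexamethasone will be given at a cumulative dose of 40 mg/week". Two schedules follow. One is "20 mg/day at Days 1, 4, 8, 11, 15, 18, 22 and 25 in a 28-day cycle". The other is "20 mg/day at Days 1, 4, 8, 11, 15, and 18 in a 21-day cycle (regimen with drug holiday".

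Section 6.6 refers to Tables 14A and 14B together for toxicities judged strictly related to dexamethasone.

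- Table 14A works by toxicity. Its gastrointestinal row for Grade 1-2 events says to "reduce dexamethasone by 50% (eg., 20 mg per week to 10 mg per week". Its insomnia row says to "reduce the dose by 50% (eg., 20 mg to 10 mg to 5 mg". The edema row steps from 10 mg to 5 mg after a first halving. The row on confusion or mood also allows a further step to 5 mg.
- Table 14B works by step. The first is "Reduce dexamethasone by 50% from starting dose", the second is "Give dexamethasone only on Day 8, 15, 21", and the third is to stop the drug.

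Section 6.6 also allows institutional guidelines in place of the tables and requires every modification to be discussed with the sponsor's medical lead. Section 6.9.1 allows deviation on clinical judgement after discussion with the medical monitor.

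**The concern.** A reduction rule has to map onto the schedule that it reduces, and here it does not in three places.

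- **Days.** Table 14B keeps a day on which no dexamethasone is scheduled in either cycle. A site cannot tell whether to give a dose on a new day, move a scheduled one, or give only the two listed days that exist. Nor does the step say how many mg to give.
- **Units.** One row of Table 14A counts in mg per week from a base that is not the protocol's weekly dose. Other rows count in mg per administration from a base that is.
- **Precedence.** After a first halving, Table 14A lowers the amount per dose and Table 14B lowers the number of days. Both are cited as the guidance, and nothing says which applies when they differ.

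Dexamethasone is itself part of the combination that Part B was to assess for tolerability and response. If the same toxicity can lead to different steroid doses depending on how a table is read, exposure to the background drug is harder to interpret.

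**Working it through.** **Inputs.** From Section 4.1: 20 mg per administration, with 8 dosing days in 28 days (1, 4, 8, 11, 15, 18, 22, 25) or 6 in 21 days (1, 4, 8, 11, 15, 18). From Table 14B: a 50% first cut, then Days 8, 15 and 21. From Table 14A: 20 to 10 mg per week (gastrointestinal), and 20 to 10 to 5 mg (insomnia).

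**1. The stated weekly dose.** Weekly dose = mg per administration x dosing days / weeks in the cycle.

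- 28-day cycle: 20 x 8 = 160 mg; 160 / 4 = 40 mg/week.
- 21-day cycle: 20 x 6 = 120 mg; 120 / 3 = 40 mg/week.

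The protocol's 40 mg/week is reproduced in both.

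**2. Days.** Days 8 and 15 are on both lists. Day 21 is on neither.

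**3. First reduction.** Half of 40 is 20 mg/week (80 mg per 28-day cycle, 60 mg per 21-day cycle). The gastrointestinal example starts at 20 / 40 = 50% of the schedule and ends at 10 / 40 = 25%. The insomnia sequence, taken per administration, is 100%, 50% and 25% of 20 mg, so it fits.

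**4. Second reduction.** Percent of start = mg per cycle under the reading / 160 (28-day) or / 120 (21-day).

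| Reading of the second step | 28-day cycle | 21-day cycle |
|---|---|---|
| Table 14A: 5 mg on every scheduled day | 5 x 8 = 40 mg, 25% | 5 x 6 = 30 mg, 25% |
| Table 14B: three days, halved dose kept | 3 x 10 = 30 mg, 18.75% | 3 x 10 = 30 mg, 25% |
| Table 14B: Day 21 skipped, halved dose kept | 2 x 10 = 20 mg, 12.5% | 2 x 10 = 20 mg, 16.7% |
| Table 14B: three days at 20 mg | 3 x 20 = 60 mg, 37.5% | 3 x 20 = 60 mg, 50% |
| Table 14B: Day 21 skipped, 20 mg | 2 x 20 = 40 mg, 25% | 2 x 20 = 40 mg, 33.3% |

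The readings run from 12.5% to 50% of the starting dose. The 50% entry equals the first step (60 mg per 21-day cycle), so on that reading the second reduction reduces nothing. Without that one entry the range is 12.5% to 37.5%. If the halved dose is taken to persist throughout, it is 12.5% to 25%.

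**The case against.** The best defence is that the tables are guidance within a wider system. Institutional guidelines may replace them, deviation on clinical judgement is allowed, each modification is to be discussed with the sponsor, and overlapping toxicity leads first to a reduction of M3258. Variation between sites is therefore permitted by design and would survive a corrected table. This stands, and it rules out saying that sites *would* cut by different amounts because of the mismatch; the text supports only that they could. It does not remove the contradiction, because sponsor discussion cannot show which reading the protocol intends.

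Table 14A is also not off-schedule as a whole. The insomnia and edema rows fit 20 mg per administration. The gastrointestinal figure is marked as an example and could describe someone already halved to 20 mg/week, although the row does not say so. The defect there is one row in other units from another base.

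The top of the range is a strained reading too: it restores 20 mg per dose under a column labelled as a second reduction. The narrower ranges in the working allow for this.

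A reader might go further and infer that the table conflict decides who is evaluable for DLT and who enters the Part B stopping denominators. Section 9.3 asks for "80% of planned administrations of each treatment during the DLT period and completed the DLT period", together with 80% of the planned cumulative dose, and a mid-cycle halving does leave less: after 4 of 8 doses, (4 + 4/2) / 8 = 75%; after 3 of 6, (3 + 3/2) / 6 = 75%. But a perfectly written 50% cut gives the same 75%, and one dose later the figures are (5 + 3/2) / 8 = 81% and (4 + 2/2) / 6 = 83%. Participants with a DLT stay in the set whatever they received. Section 7.1 counts evaluable participants without tying that word to the Section 9.3 set. The effect belongs to the separate each-treatment criterion and does not follow from Tables 14A and 14B.

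**Conclusion.** The contradiction holds on the text. Table 14B names a day that is on neither dexamethasone schedule and leaves the dose for that step open. One row of Table 14A starts from half the scheduled weekly dose. The two tables diverge at the second step with no order of precedence. The size is a second-step dose anywhere from 12.5% to 50% of the start, or 12.5% to 25% if the first halving is assumed to continue. These figures assume a full cycle at the reduced step and the day lists of Section 4.1.

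This is an internal inconsistency in a dosing rule. No sample size, power or error rate depends on it, and the documents do not support a claim about DLT evaluability or stopping boundaries on this ground. SAP Section 7 records that the study stopped before Part B began, so no participant was treated under these tables. The point applies to the protocol text and to any later protocol that reuses it.

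**What to change.** The sponsor should reconcile Section 4.1 with Tables 14A and 14B so that:

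- the days named in each reduction step agree with the dexamethasone schedule for each cycle length;
- one unit is used throughout, with every example consistent with the protocol's starting dose;
- the second step states the dose per administration and whether the first cut persists;
- one sentence says which table governs when both apply, and how they relate to institutional guidelines.

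Which days and doses are right is for the sponsor to decide; none is proposed here. The cost is a wording change to two tables and, if needed, the matching lines of Section 4.1 and the synopsis. It needs no new data, participants or analyses. Because Part B was not run, no change to the SAP follows from this point.

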6.7 Study Intervention at the End of the Study

Not applicable.

6.8 Special Precautions

Monitoring of neuropathic pain and/or peripheral sensory or motor neuropathy beyond DLT period in escalation phase and continuously in expansion phase.

6.9 Management of Adverse Events of Special Interest

An AESI (serious or nonserious reaction) is one of the scientific and medical concern specific to the study intervention, for which ongoing monitoring and rapid communication by the

Investigator to the Sponsor will be encouraged. Such events of interest may require further investigation or in-depth evaluations to better characterize and understand the association between the adverse event and M3258. Based on nonclinical data, following AEs will be considered AESI ([Table 15](#)).

Table 15 Adverse Events of Special Interest

AE	Management
Myelosuppression (Grade > 3) with complications i.e., cytopenia, febrile neutropenia, thrombocytopenia with clinically significant bleeding	Repeat blood test within 72 hours See Table 12 for guidance on dose modification.
Clinically significant GI Hemorrhage	Routine monitoring of clinical signs and symptoms Symptomatic treatment at Investigator's discretion See Table 13 for guidance on dose modification
GI Mucositis (Diarrhea, vomiting)	Monitor signs and symptoms. Symptomatic treatment at Investigator's discretion is allowed See Table 13 for further guidance.
Opportunistic infections including COVID-19	Monitor signs and symptoms; Testing for COVID-19 according to local medical practice Symptomatic treatment per local medical practice.
Allergic/Hypersensitivity Reaction/Skin Rash	Advised to manage participant in accordance to standard local practice. Premedication (antihistamine/corticosteroid) for the same and/or subsequent participants may be considered if appropriate based on Investigator's clinical judgement limiting dexamethasone to doses not reaching the level required for the treatment of multiple myeloma.

AE = Adverse event, GI = Gastrointestinal.

Investigator must complete the AESI Report Form and communicate with the Sponsor within 24 hours of occurrence of AESI. Serious AESI (based on SAE reporting criteria) should always be reported as SAE as outlined in [Section 8.2](#).

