- Hy's law: Evidence of hepatocellular toxicity without clear alternative reason to explain the observed liver-related laboratory abnormalities, such as increase in AST or ALT of ≥ 3 x

ULN elevation and elevation of serum total bilirubin $\geq 2 \times$ ULN, without initial findings of cholestasis (elevated serum ALP) or other apparent clinical causality (eg viral hepatitis A, B, C or co-medication)

- Any death not clearly due to the underlying disease or extraneous causes
- Any Grade ≥ 4 hematologic AE, and:
 - Grade ≥ 3 febrile neutropenia with ANC $<1000/\text{mm}^3$ and a single temperature of $>38.3^\circ\text{C}$ (101°F) or a sustained temperature of $\geq 38^\circ\text{C}$ (100.4°F) for more than 1 h
 - Grade ≥ 3 thrombocytopenia with medically concerning bleeding
 - Grade 4 thrombocytopenia lasting >7 days, or platelets $<10,000/\text{mm}^3$ at any time

Except:

- Isolated Grade 4 lymphopenia without clinical correlate
- Any Grade 4 neutropenia of < 7 days duration not associated with any clinical symptoms.

- Neuropathic Pain or Peripheral Sensory or Motor Neuropathy:
 - Any aggravation by 2 grades or any Grade ≥ 3 (severe symptoms: limiting self-care Activity of Daily Life [ADL]).
- Any TEAE the SMC deems clinically relevant, that impairs daily function or abnormality occurring in participants treated with M3258 -/+ combination with dexamethasone at any time in Cycle 1 and any toxicity at any time in Cycle 1
- A study intervention-related TEAE (observed in subsequent cycles) that in the opinion of the SMC is of potential clinical significance such that further dose escalation would expose participants to unacceptable risk.

Any DLT will be confirmed by the SMC.

Table 11 describes the recommended individual dose modifications related to M3258-related neuropathic pain or peripheral sensory or motor neuropathy when experienced by participants outside of DLT period. **Table 12** describes the individual dose modifications and temporary or permanent treatment discontinuations for M3258-related hematologic toxicities when experienced by participants outside of DLT period. **Table 13** describes the individual recommended temporary treatment discontinuations for M3258-related general toxicities when experienced by participants outside of DLT period.

Table 11 Recommended Dose Modification for New Onset or Worsening Neuropathic Pain and/or Peripheral Sensory or Motor Neuropathy (outside of DLT Period)

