Severity of Peripheral Neuropathy Signs and Symptoms ^a	Modification of Dose and Regimen
Grade 1 (asymptomatic: loss of deep tendon reflexes or paresthesia) without pain or loss of function	No action
Grade 1 with pain or Grade 2 (moderate symptoms: limiting instrumental ADL ^b)	Reduce M3258 dose by one dose level (based on dose escalation part) or at least by 50% if no lower dose level is available
Grade 2 with pain or Grade 3 (severe symptoms: limiting self-care ADL ^c)	Withhold M3258 therapy until toxicity resolves to Baseline or Grade 1 without pain, then reinitiate with a reduced dose of M3258 by one dose level (based on dose escalation part) or at least by 50% if no lower dose level is available If recurrence to Grade 2 with pain or higher, permanently discontinue M3258.
Grade 4 (life-threatening consequences: urgent intervention indicated)	Permanently discontinue M3258.

ADL = Activities of daily living; DLT = Dose-limiting toxicity; NCI = National Cancer Institute.

a Grading based on NCI Common Terminology Criteria for Adverse Events (CTCAE) v5.0.

b Instrumental ADL: refers to preparing meals, shopping for groceries or clothes, using telephone, managing money etc.

c Self-care ADL: refers to bathing, dressing and undressing, feeding self, using the toilet, taking medications, and not bedridden.

Table 12 Dose Modifications and Temporary/Permanent Treatment Discontinuation for Hematologic Toxicity (outside of DLT Period)

Hematologic Toxicity	Dose Modification
Neutropenia Grade 3 (without complications)	No dose reduction, consider treatment with G-CSF
Grade 3 Neutropenia associated with fever ($\geq 38.5^{\circ}\text{C}$) or neutropenia Grade 4	Hold M3258 until recovery to Baseline OR \leq Grade 2. Upon recovery, restart M3258 at current dose and consider G-CSF support. If recurrence is seen, reduce M3258 by one dose level (based on dose escalation part) or at least by 50% if no lower dose level is available. If second occurrence, permanently discontinue dosing
Thrombocytopenia Grade 3 (without complications)	No dose reduction required
Platelet count $< 25,000 / \mu\text{L}$ (i.e., Grade 4) or Grade 3 thrombocytopenia with bleeding	Hold M3258 until recovery to Baseline Or \leq Grade 2. Upon recovery, restart at a dose which is one dose level lower (based on dose escalation part) or at least by 50% if no lower dose level is available.

DLT = Dose limiting toxicity; G-CSF = granulocyte-colony stimulating factor.

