8.3.3 Follow-Up of Adverse Events and Serious Adverse Events

AEs are recorded and assessed continuously throughout the study, as specified in Section 8.3.1 and are assessed for their outcome at the 30-Day Follow-Up Safety Visit. All SAEs ongoing at

the 30-Day Follow-Up Safety Visit must be monitored and followed up by the Investigator until stabilization or until the outcome is known, unless the participant is documented as “lost to Follow-Up”. Reasonable attempts to obtain this information must be made and documented. It is also the responsibility of the Investigator to ensure that any necessary additional therapeutic measures and Follow-Up procedures are performed. Further information on Follow-Up procedures is given in [Appendix 5](#).

Based on the nonclinical toxicology studies, adverse events of myelosuppression, GI toxicity, opportunistic infections and allergic reactions are considered AESI (Section [6.9](#)). These events must be reported on AESI Forms to Merck Healthcare Global Patient Safety throughout the study until resolution or permanent outcome of the event.

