15.3.3 Other Significant Adverse Events

A listing of AEs of special interest (AESI) will be provided. This will be sorted by dose level and participant. This listing will additionally contain age, sex, , SOC, PT, grade, SAE (yes/no), DLT

per investigator/SMC (yes/no), relatedness to M3258 (yes/no),, start date (+treatment day), stop date (+treatment day), duration (in days), action taken with M3258, if treatment was stopped before start of AE: days since stop of treatment, and outcome.

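### The grade limit on the myelosuppression AESI in Table 15 disagrees with Section 8.3.3 and with the Table 12 rows it cites, so Grade 3 complicated cytopenias may be left out or reported inconsistently as AESIs (low severity)

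*Protocol*

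**What the plan says.** Protocol Section 6.9 introduces Table 15 with the words "following AEs will be considered AESI", so the table is the operative definition. Its first row reads "Myelosuppression (Grade > 3) with complications i.e., cytopenia, febrile neutropenia, thrombocytopenia with clinically significant bleeding". For management, the row asks for a repeat blood test within 72 hours and refers to Table 12.

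Table 12 (Section 6.6) applies outside the DLT period. One row starts with "Grade 3 Neutropenia associated with fever"; another includes Grade 3 thrombocytopenia with bleeding.

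Section 8.3.3 states that "adverse events of myelosuppression, GI toxicity, opportunistic infections and allergic reactions are considered AESI", gives no grade, refers back to Section 6.9, and requires AESI forms until the event resolves or its outcome is permanent.

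The DLT list in Section 6.6 includes "Grade ≥ 3 febrile neutropenia with ANC" below 1000/mm³ plus a temperature criterion, and "Grade ≥ 3 thrombocytopenia with medically concerning bleeding".

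On the analysis side, SAP Section 15.3.3 says "A listing of AEs of special interest (AESI) will be provided" and names the columns. It gives no grade rule, term list or derivation. The SMC analysis plan appended to the SAP (its Section 15.7) plans a similar listing, also without a rule.

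**The concern.** AESI status has one distinct job in this protocol: it brings nonserious events to the sponsor within 24 hours on their own form (Section 6.9 and Appendix 5) and keeps them under follow-up. Serious AESIs go through the SAE route anyway. A definition that starts above Grade 3 therefore covers mostly events that are already SAEs. The nonserious Grade 3 events, where the AESI route would add something, fall outside it.

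Table 15 also names febrile neutropenia and thrombocytopenia with significant bleeding, and sends the reader to Table 12 rows that treat those conditions at Grade 3. A site reading Table 15 and a site reading Section 8.3.3 could classify the same event differently. The listings for the clinical study report and for the SMC would carry that difference forward without showing it.

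**Working it through.** No sample size, error rate or event count is involved, so there is nothing numerical to reproduce. The check compares the grade ranges.

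| Place | What it governs | Grades covered | Grade 3 febrile neutropenia, or Grade 3 thrombocytopenia with bleeding |
|---|---|---|---|
| Protocol Table 15 | AESI definition | above 3, so 4–5 | out |
| Protocol 8.3.3 | AESI statement and form duty, referring to 6.9 | no limit | in, if read alone |
| Protocol Table 12 | dose modification outside the DLT period, cited by Table 15 | includes Grade 3 with fever or bleeding | in |
| Protocol 6.6, DLT list | DLT status | 3 and above, so 3–5 | in |
| SAP 15.3.3; SMC plan 15.7 | AESI listings | none stated | depends on how the event was flagged |

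Only the first two rows speak to AESI status. Taking Grades 4–5 from Grades 3–5 leaves exactly Grade 3 as the set in dispute.

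Four typical Part A records show where this matters:

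1. **Nonserious Grade 3 febrile neutropenia in Cycle 1 that meets the DLT criteria.** Appendix 5 requires it in the CRF within 24 hours as a DLT. AESI: no under Table 15, yes under Section 8.3.3. There is little practical loss.
2. **The same event in Cycle 2 or later.** Section 6.6 ties the DLT period to the first cycle; later events count only if they are related to study intervention and the SMC judges them significant for further escalation. The event is not an SAE. AESI: no under Table 15, yes under Section 8.3.3. This is the real gap, and Table 12 is written for this period.
3. **Grade 4 febrile neutropenia.** Section 6.9.1 sends Grade 4 toxicity to the sponsor as an SAE within 24 hours, and Appendix 5 makes clinical Grade 4 and 5 events SAEs. It is an AESI under both sections, but the AESI label adds almost nothing.
4. **Grade 3 thrombocytopenia with a clinically significant GI hemorrhage.** It enters through the separate GI hemorrhage row of Table 15, which has no grade limit. A bleed elsewhere is treated as in record 2.

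One qualification on record 3: Appendix 5 treats a Grade 4 laboratory abnormality as serious only if it meets a seriousness criterion, whereas Section 6.9.1 makes no such exception. The row as written therefore keeps a small function, not none.

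Record 2 still reaches the data. SAP Section 15.2.1 lists all adverse events of Grade 3 or higher together with SAEs, and Section 15.3.1 of the SMC plan does the same. What may be missing is the 24-hour AESI report and a consistent AESI flag.

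**The case against.** The strongest reply is that there is only one AESI threshold. Section 8.3.3 shortens the other categories too and refers back to Section 6.9, so it reads as a summary of Table 15. Section 6.6 and Table 12 do not define AESIs, and nothing requires a DLT to be an AESI: Grade 3 or higher neuropathy and Hy's law are DLTs and are not in Table 15. The summary of changes shows that this row was edited in the current amendment with its grade limit kept, so the limit may be deliberate. The events are also caught elsewhere, as DLTs, SAEs or listed Grade 3 or higher events.

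Much of this stands. A mismatch with the DLT list alone would not be an error, and it is not the basis of this point. What remains is that Section 8.3.3 carries its own form duty in ungraded wording, that Table 15 points to Grade 3 guidance for conditions its own limit excludes, and that the limit leaves the row mostly duplicating SAE reporting. The back-reference suggests an answer to the first of these but does not address the other two.

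A reader might infer that Grade 3 events are absent from AESI reporting and from the AESI listings. The documents do not support that. Section 8.3.3 and the named complications could lead sites to report them, and neither listing applies a grade filter. Nor can a reader conclude that myelosuppression is the toxicity the protocol most expects, because the nonclinical safety text is redacted.

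**Conclusion.** The inconsistency is real and of low severity. Nonserious Grade 3 complicated cytopenias, mainly after Cycle 1, may be left out of 24-hour AESI reporting or flagged differently by site, and the two AESI listings inherit that. The documents give no event rates, so the number of affected events cannot be stated.

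The consequence is bounded. The SAP plans an AESI listing and no AESI rate. The Bayesian model and the MTD suggestion use DLTs as decided by the SMC, so the DLT analysis and dosing decisions are unaffected. SAP Section 7 reports that the study stopped before Part B began, so the practical effect is on Part A and its study report.

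The conclusion assumes that Grade > 3 is meant literally, and that the AESI listings draw on what sites flag, since no other derivation is given.

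**What to change.** Reconcile Table 15 and Section 8.3.3 to one reporting threshold for the myelosuppression AESI. Grade 3 or higher with complications would match the complications Table 15 names and the Table 12 rows it cites. If the higher limit is intended, Section 8.3.3 should repeat it, and the reason for excluding Grade 3 should be given.

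Add a sentence to SAP Section 15.3.3, and to the SMC plan, saying how AESIs are identified: by site flag, or by a derivation from preferred term and grade. A derivation could be applied to adverse events already recorded, whatever the sites flagged.

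This changes reporting only and touches no dose or treatment rule. The cost is one symbol in Table 15, a clause in Section 8.3.3, a sentence in each analysis plan, and slightly more AESI forms.
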